## **2.2.2 Economic aims and objectives**

### **Primary Objective**

An economic evaluation conducted alongside a clinical trial, assessing cost-effectiveness over a 90 day period from an NHS and personal social service cost perspective.

### **Secondary Objectives**

- Cost-effectiveness over 90 days from an NHS, personal social service and societal cost perspective
- Extrapolation of trial outcomes to establish cost-effectiveness over a lifetime horizon from an NHS cost perspective
- Expected Value of Information analysis to quantify the maximum amount a decision-maker would be willing to pay for eliminating all uncertainty in the economic results.

## 3. TRIAL DESIGN AND SETTING

### 3.1 Trial design

The TONIC trial is a multi-centre, two-arm, parallel group, superiority, individual participant-RCT with 1:1 allocation to early PN or standard nutritional care with an internal pilot and a full economic evaluation. Patients undergoing NELA eligible emergency laparotomy or laparoscopy will be randomised to either early PN started within 48 hours of emergency laparotomy/laparoscopy or standard nutritional care.

### 3.2 Trial setting

The study will be conducted in approximately 25 NHS hospitals across the United Kingdom (UK) providing emergency surgical services, which have a nutritional support team.

### 3.3 Sub-studies

There are no planned sub-studies.

### 3.4 Assessment of risk

Participants in both arms will be undergoing emergency laparotomy/laparoscopy as part of their standard medical care. The trial intervention is PN with the main risks relating to changes in blood electrolytes, high blood sugar, liver function changes (cholestasis), and potential infection of the peripherally inserted central catheter (PICC) line. These risks are generally manageable and monitored closely by healthcare professionals to prevent any lasting impact. The risks of PN will be mitigated through regular monitoring and adjustments of blood electrolytes and blood sugar levels, careful management of liver function and strict infection control measures for the PICC line.

All clinical trials can be considered to involve an element of risk and in accordance with the Birmingham Clinical Trials Unit (BCTU) standard operating procedures this trial has been risk assessed to clarify any risks relating uniquely to this trial beyond that associated with usual care. A Risk Assessment has been conducted and concluded that this trial corresponds to the following categorisation: No higher than the risk of standard medical care.

## 4. ELIGIBILITY

### 4.1 Inclusion criteria

- Adult patients aged 18 years and over
- Scheduled for NELA eligible expedited, urgent or immediate emergency laparotomy or laparoscopy according to National Confidential Enquiry into Patient Outcome and Death NCEPOD criteria (see Table 1)
- Able to give informed consent, with interpreters where necessary OR personal consultee (England & Wales)/legal representative (Scotland) provides declaration/consent if a patient temporarily lacks capacity.

**Table 1: NCEPOD criteria for urgency of surgery**[30]

| Term             | Definition  |
|------------------|---|
| Immediate | Immediate life, limb or organ-saving intervention – resuscitation simultaneous with intervention. Normally within minutes of decision to operate. Life-saving Other e.g. limb or organ saving   |
| Urgent    | Intervention for acute onset or clinical deterioration of potentially life-threatening conditions, for those conditions that may threaten the survival of limb or organ, for fixation of many fractures and for relief of pain or other distressing symptoms. Normally within hours of decision to operate. |
| Expedited | Patient requiring early treatment where the condition is not an immediate threat to life, limb or organ survival. Normally within days of decision to operate.  |

### 4.2 Exclusion criteria

- Undergoing trauma-related laparotomy or laparoscopy
- Being treated with palliative/end of life intent
- Abdominal surgery in the preceding 30 days.
- On long term PN prior to admission

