## **Intervention and Comparator**

The intervention is early PN started within 48 hours of emergency laparotomy or laparoscopy. The control arm is standard nutritional care which can include a combination of oral nutritional supplements, nasoenteric feed, or no additional nutritional support. PN is permitted in the control arm, but should not be started before five days after surgery, unless otherwise indicated, in line with NICE guidance.

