## 1. BACKGROUND AND RATIONALE

### 1.1 Background

Around 21,000 people undergo major emergency abdominal surgery each year in England and Wales[1]. Emergency laparotomy involves an incision in the centre of the abdomen to provide access to abdominal organs and is used to treat intra-abdominal sepsis, perforated viscus, obstruction, and ischaemia. These conditions have high morbidity (up to 47%[2]) and mortality (between 9-18%) rates[3]. Work by the National Emergency Laparotomy Audit (NELA) has improved outcomes in emergency laparotomy, through early commencement of antibiotics, early Computerised Tomography (CT) scanning for diagnosis, timely intervention with consultant input, and stratified use of intensive care beds. This has reduced 90 day mortality for the whole emergency population from 15% to 9.6%[1]. However, the 9.6% mortality rate represents a plateau, with no improvement since 2021, suggesting that current approaches may have reached their maximum benefit. Therefore, we need to change other aspects of the treatment pathway by introducing new interventions.

A good candidate intervention would be one that is widely available, with common processes to deliver, and a known risk profile. One such intervention is parenteral nutrition (PN), which is a method of delivering nutrition intravenously. This bypasses a non-functioning gut (common in emergency surgical conditions), to directly deliver nutrients via blood, and does not rely on patient appetite to ensure delivery of calories and nutrients[4]. PN is often delivered following emergency laparotomy[5, 6]; as patients struggle to meet nutritional requirements through enteral routes following surgery, with frequent interruptions[7]. Pilot work also shows that patients spend an average of seven days without enteral nutrition prior to emergency laparotomy[8]. This exacerbates malnutrition, which affects 30% of patients on admission to hospital [9], and 20-30% will see their nutritional status deteriorate during their admission[10]. Malnutrition causes impaired wound healing, poor immune function[11], and higher rates of complications and death after surgery[12].

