### 6.3 Randomisation process

Randomisation should be performed pre-operatively for all participants.

Randomisation will be provided by BCTU using a secure online Electronic Data Capture (EDC) system (available at <https://bctu-redcap.bham.ac.uk/>), thereby ensuring allocation concealment. Unique log-in usernames will be provided to those who wish to use the online EDC system and who have been delegated the role of randomising participants into the trial as detailed on the TONIC Site Signature and Delegation Log. These unique log-in details must not be shared with other staff and in no circumstances should staff at sites access the system using another person's login details. The online EDC system will be available 24 hours a day, 7 days a week, apart from short periods of scheduled maintenance.

In the rare instance of the online system being unavailable, the trial office should be contacted and are available Monday to Friday, 09:00 to 17:00 UK time, except for bank holidays, government guided closures and University of Birmingham (UoB) closed days.

**Please note: to randomise a patient when the online system is unavailable, the TONIC Trial Office should be contacted directly via email or telephone using the contact details outlined at the front of the protocol.**

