## **7.9 Adherence**

We will assess adherence in the intervention arm by reporting the percentage of participants who receive PN within 48 hours post-operation. Commencement of the intervention within the 48 hour timeframe is considered adherent and will be monitored centrally.

We will also assess adherence to the control group allocation by monitoring for cross-over to early PN in the control arm. Any participant in the control arm who receives PN within 5 days post-operatively is considered non-adherent.

Adherence to randomised allocation will be assessed in both arms. Sites will be monitored for PN use, and duration of use to identify potential cross-over risks. For the intervention arm, we will record use of PN, including number of bags/calories received. This information will be taken from clinical notes by the research team. We will record other nutritional interventions, their type and frequency. For the control arm, we will record use of nutritional interventions, their type and frequency. If PN is used, we will note its date of commencement and reason for administration. Adherence to intervention relies on commencement of PN within 48 hours post-operation. Adherence to control means no PN used until day 5.

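### The eligibility criteria let in patients whose PN was started earlier in the same admission, and the arm and adherence definitions do not fit them

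*Protocol*

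**What the plan says.** The only exclusion that mentions PN, in section 4.2 and repeated in the Trial Summary, is "On long term PN prior to admission". Another exclusion, "Abdominal surgery in the preceding 30 days", removes some patients who might be on PN for other reasons. Nothing in 4.1 or 4.2 deals with PN started during the current admission.

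Section 6.3 states: "Randomisation should be performed pre-operatively for all participants". Table 1 in section 4.1 makes expedited surgery eligible and describes its timing as "Normally within days of decision to operate".

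Section 7.1 defines the intervention as PN commencing within 48 hours of the operation. For the control arm the Trial Summary says "PN is permitted in the control arm, but should not be started before five days after surgery", and the sentence goes on to allow an exception where PN is otherwise indicated. Sections 1.2.3, 7.1 and 7.3 word the exception as pressing clinical need. Section 1.2.3 gives three examples: emergency reintervention, unplanned escalation to intensive care, and enterocutaneous fistula.

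Section 7.9 makes intervention-arm adherence depend on PN commencing within 48 hours after the operation. For controls it says: "Any participant in the control arm who receives PN within 5 days post-operatively is considered non-adherent".

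The estimand in Table 15 uses a treatment-policy strategy for non-compliance and switching. In Table 3 the pilot cross-over criterion is green at 0%, amber up to 10% and red above 10%.

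**The concern.** The trial compares times of starting PN after an operation. A patient already receiving PN when randomised has no start left to time. Consider a patient admitted with obstruction, given PN on the ward while non-operative care is tried, and then booked for an expedited laparotomy. This patient meets the inclusion criteria and no exclusion.

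Three things are at stake. The first is the contrast: if PN continues whatever the allocation, the participant contributes no difference in PN timing to the intention-to-treat mean. The second is classification: the same patient in the control arm is recorded as non-adherent because of a state that existed before randomisation, and this feeds the cross-over figures used in the pilot decision. The third is the meaning of the comparator: if a site stops running PN to follow the control rule, that participant receives PN withdrawal, which is not what the objective describes as usual nutritional care.

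**Working it through.** **Step 1. Can the patient be randomised?** PN begun this admission is not long-term PN before admission. If there was no abdominal surgery in the previous 30 days, no other exclusion applies. Randomisation precedes surgery, so PN status is known when eligibility is checked. The baseline items in Table 4 do not include it. Table 4 does record PN with its commencement date during the hospital stay, but no rule says how a date before the operation is to be treated. The patient is eligible as written.

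**Step 2. How do the definitions apply?**

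| Allocation | What happens to running PN | Result under the protocol |
|---|---|---|
| Early PN | Continues | No post-operative commencement to judge against 48 hours; time from operation to starting PN (8.2.2.1) is negative or undefined |
| Control | Continues | PN received before day 5, so non-adherent under 7.9 |
| Control | Stopped | Adherent, but the care given is PN withdrawal |

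Section 7.9 also varies its own wording for the intervention arm. It first speaks of participants who receive PN within 48 hours, then of commencement within 48 hours. PN already running satisfies the first and not clearly the second.

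**Step 3. Reproduce the sample size.** Inputs from section 14.1: difference 6 CCI points, SD 27, two-sided 5%, power 90%, attrition 5%.

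- n per arm = 2 × (1.960 + 1.282)² × 27² / 6² = 425.5, rounded up to 426.
- 426 / 0.95 = 448.4, rounded up to 449 per arm, 898 in total. This matches the protocol.
- Evaluable per arm: 449 × 0.95 = 426.55. SE = 27 × √(2/426.55) = 1.849. Power = Φ(6/1.849 − 1.960) = 90.1%.

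**Step 4. Dilution.** Assumption: a share p of participants receive the same PN in both arms and have zero effect, with the SD held at 27. The expected difference is then 6 × (1 − p), and power is Φ(6(1 − p)/1.849 − 1.960). The protocol gives no value for p, so a range is shown.

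| p | Participants (898 × p) | Expected difference | Power at 898 | Total N for 90% power |
|---|---|---|---|---|
| 0 | 0 | 6.00 | 90.1% | 898 |
| 1% | 9 | 5.94 | 89.5% | 916 |
| 2% | 18 | 5.88 | 88.9% | 936 |
| 5% | 45 | 5.70 | 86.9% | 994 |
| 10% | 90 | 5.40 | 83.2% | 1,108 |

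**Step 5. Pilot.** Section 8.1 aims for 60 participants, about 30 of them controls. A single control participant whose PN continues means the 0% needed for green on cross-over is missed.

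**The case against.** The best reply is that the control rule is not absolute. The Trial Summary allows earlier PN where otherwise indicated, and the examples of pressing need in 1.2.3 are illustrative, so a clinician may continue PN in a control participant. Section 7.9 then has the start date and reason recorded. This stands as far as care is concerned. It does not settle classification, because the control-arm sentence in 7.9 has no exception: PN within five days is non-adherent whatever the reason.

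The second reply is that such patients will be few. This largely stands. Section 5.2 gives median admission-to-surgery times of 10, 17 and 34 hours for the 2-, 6- and 18-hour categories, which leaves little time to start PN. Expedited cases may wait longer, but no figure is given for them. Section 1.1 reports that "patients spend an average of seven days without enteral nutrition prior to emergency laparotomy", yet it does not say that those days were spent in hospital or that PN was given. Its statement that PN is often used refers to the period after laparotomy. The 30-day surgery exclusion removes some further candidates.

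The third reply is that broad entry is deliberate (1.2.1), with cross-over monitored and a treatment-policy estimand. That is a fair reason to keep these patients if the sponsor wishes, but the definitions would then have to cover them.

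A reader might infer that the arms cannot differ at all for these patients. The documents do not support that: if control PN is stopped, the arms do differ. A reader might also infer that the complier analysis is distorted. That cannot be shown either, since 14.2.1 leaves its adherence definition to the SAP and some non-compliance is what such an analysis is meant to handle.

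**Conclusion.** The gap is in the text. Patients already on PN this admission are eligible, and the arm and adherence definitions do not say what they are to receive or how they are to be counted. Depending on what the site does, such a participant adds no PN-timing contrast, is counted as control-arm cross-over, or is compared with PN withdrawal.

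The likely effect on power is small. At 1% to 2% affected the loss is about one percentage point or less; it reaches roughly three points at 5% and seven at 10%. These figures rest on an assumed p, on PN continuing in both arms with zero effect, and on an unchanged SD. Nothing in the protocol supports any particular p, so one cannot conclude that the trial is underpowered. The stated 898 is correct for its own inputs. The case for acting rests on the undefined classification and the low cost of removing it.

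**What to change.** Extend the fourth exclusion, in section 4.2 and the Trial Summary, to patients receiving PN at the time of randomisation, including PN started during this admission, alongside those on long-term PN. Add the question to the electronic eligibility form. The sample size stays as it is. The cost is a wording change in two places and one form item, with a slightly smaller eligible pool and a slightly narrower pragmatic population.

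If the sponsor prefers to keep these patients, record PN status at randomisation as a baseline item, and reconcile 4.2 with 7.1, 7.9 and the cross-over criterion in Table 3 so that PN already running is classified in the same way throughout. Whether such PN should continue or stop is a clinical matter on which this review takes no position.

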### 4.3 Co-enrolment

Co-enrolment is permitted to observational or biomarker studies (non-interventional studies). Co-enrolment in other interventional trials is NOT permitted.

## 5. CONSENT

The majority of patients undergoing emergency laparotomy or laparoscopy will be able to provide fully informed consent. There are, however, a proportion of patients who meet the inclusion criteria for the study who are either unable to provide full consent or are not able to consent at all due to a temporary impairment resulting from the indication for their emergency laparotomy or laparoscopy. Patients may be unconscious, critically unwell, distracted by pain or anxiety, or have received large doses of opiates for pain relief, potentially affecting their ability to process information. The methods of gaining consent for inclusion in the study are different for patients who are able to provide consent and those who are not. The law around recruitment of patients that lack capacity is governed under the Mental Capacity Act in England and Wales and by Adults with Incapacity (Scotland) Act in Scotland. The terminology within each Act is different and as a result Section 5.3 of this protocol will explain the process for including patients without capacity in England and Wales and Section 5.4 will cover patients in Scotland.

Due to the nature of emergency laparotomy or laparoscopy, the time from the patient being approached for participation in the study and recruitment may be limited. There is therefore no minimum time between the patient (or consultee/representative) being given the information sheet for the trial and consent being obtained. This has been subject to consultation with patient representatives and approved by UK NHS research ethics committees (REC).

### 5.1 Patients able to provide informed consent

It is the responsibility of the Principal Investigator (PI) to obtain written informed consent for each participant prior to performing any trial related procedures. This task can be delegated by the PI to other members of the local research team (e.g. consultants, registrars, associate PI, research nurse), if local practice allows and this responsibility has been documented in the TONIC Site Signature and Delegation Log. All those delegated to take consent must have undertaken Good Clinical Practice (GCP) training.

### 5.2 Consent procedure (For patients able to provide informed consent)

A Participant Information Sheet (PIS) will be provided to facilitate the consent process. This will be supported by a short animation which covers the information from the PIS. Both the PIS and animation will be available in multiple languages. The PI or delegate will ensure that they adequately explain the aim of the trial, the trial intervention, and the anticipated benefits and potential hazards of taking part in the trial to the participant. They will also explain that participation is voluntary and that the participant is free to decide to take part and may withdraw from the trial at any time without affecting their care.

The potential participant will be given appropriate time to read the PIS and to discuss their participation with others outside of the site research team. This is flexible as the window to consent is limited by clinical urgency. The median time from admission to surgery for those categorised as needing surgery within 2, 6, and 18 hours is 10, 17, and 34 hours respectively. A flexible approach to recruitment consideration windows has been utilised in other studies (SUNRISE[31], LaCeS[32]).

The potential participant will be given the opportunity to ask questions before providing consent. If the participant then expresses an interest in participating in the trial, they will be asked to sign and date the latest version of the Informed Consent Form (ICF). The PI or delegate will then sign and date the ICF.

A copy of the ICF will be given to the participant, a copy will be filed in the medical notes and the original placed in the Investigator Site File (ISF). Once the participant is entered into the trial, the participant's trial number will be entered on the ICF maintained in the ISF. In addition, the participant understands and acknowledges that, a copy of the signed ICF will be transferred to the trial team at BCTU for review.

Consent will be obtained to collect contact details and use the participant's preferred contact details, i.e., e-mail address, mobile number, and/or postal address for the purpose of sending participants either online links to complete the electronic questionnaires or hard paper copies depending on what is preferred by the participant.

Details of the informed consent discussions will be recorded in the participant's medical notes. This will include date of discussion, the name of the trial, summary of discussion, version number of the PIS given to participant, version number of ICF signed and date consent received. Where consent is obtained on the same day that the trial related assessments are due to start, a note should be made in the medical notes as to what time the consent was obtained and what time the procedures started.

### **5.3 Patients unable to provide informed consent (England and Wales)**

Some patients who are eligible for the trial will have a temporary impairment to their ability to provide consent. This impairment will result from the condition for which they require surgical intervention. Patients who have a long-term cognitive impairment that prevents fully informed consent will be excluded from the trial.

If the patient does not have capacity for fully informed consent due to temporary impairment, where possible the trial will be briefly discussed with them, and they will be given the Summary PIS. In accordance with guidelines from the Health Research Authority (HRA), the trial will also be

discussed with the patient's relative or carer (Personal Consultee). The Personal Consultee will be asked if the patient has expressed any prior wishes with regard to participating in research and if the patient has expressed a preference, then this will be adhered to. The relative is not asked to provide consent on behalf of the patient but rather provide an opinion on the views and feelings of the potential participant.

The patient's relative/carer (Personal Consultee) must be:

- Told that they are being asked to advise on the views and feelings they believe the adult would have towards participation in the study
- Told that they are free to decide whether they wish to provide this advice or not
- Given sufficient information, in an understandable form, about the study to ensure that they provide informed advice

A Consultee Information Sheet will be provided to facilitate the assent process. If the consultee agrees that the patient can be included in the trial, the consultee will initial, sign and date the latest version of the Consultee Declaration Form.

If no Personal Consultee is available, the patient will not be included in the trial.

It is imperative that when a Personal Consultee has been consulted, that as soon as the participant is able to provide informed consent, the trial is explained to them and their written informed consent is sought. The participant will be given the PIS for delayed consent and their consent will be documented through the initialling, signing and dating of the latest version of the ICF for delayed consent.

If, at any stage, the participant refuses consent for involvement in the trial or asks to be withdrawn from the trial, their wishes must be adhered to. If the participant does not wish to continue, they will be withdrawn from the trial. Any data collected up to the point of withdrawal will be retained and used in the trial.

For a small number of patients (<2%), it is anticipated that they will not regain consciousness/capacity within 30 days, as these patients will have already received the intervention and reached the primary outcome, their data will be retained for use in the final analysis. If these patients regain capacity after 30 days, where practical, the local research team will consent them for their involvement in the study. In the event that the patient never regains capacity or dies, then they will remain in the trial and their data will be included in the analysis.

